5.2. General Methods

CIs for all endpoints in the statistical analysis will be presented as 2-sided at the 95% level unless specified otherwise.

The safety analyses are based on the safety population. Participants will be summarized by vaccine group according to the study interventions they actually received. The safety data will be summarized within each cohort but may also be summarized descriptively across cohorts.

For all the immunogenicity endpoints, the analysis will be primarily based on the evaluable immunogenicity population. An additional analysis will be performed based on the mITT immunogenicity population if there is a large enough difference in the number of participants included between the mITT and the evaluable immunogenicity populations.

5.2.1. Analyses for Binary Endpoints

Descriptive statistics for binary variables (eg, proportions) are the percentage (%), the numerator (n) and the denominator (N) used in the percentage calculation, and the 95% CIs where applicable.

The exact 95% CI for binary endpoints for each group will be computed using the Clopper-Pearson method.¹ For the between-group difference, the 2-sided 95% CI will be calculated using the Miettinen and Nurminen method.²

Another approach to calculate the adjusted difference in seroresponse rate or seroconversion rate between the 2 vaccine groups and the associated 95% CI will be based on the Miettinen and Nurminen method stratified by baseline NT category (< median, ≥ median) and age group (< median, ≥ median). The median of baseline NTs and age will be calculated based on the pooled data in the 2 comparator groups.

Three-Tier Approach for AE Summary

A 3-tier approach will be used to summarize AEs. Under this approach, AEs are classified into 1 of 3 tiers:

- Tier 1 events are prespecified events of clinical importance and are identified in a list in the product's safety review plan; there is no Tier 1 event identified for the study interventions at this stage.
- Tier 2 events are those that are not Tier 1 but are considered "relatively common"; a MedDRA PT is defined as a Tier 2 event if there are at least 1% of participants in at least 1 study arm reporting the event.
- 3. Tier 3 events are those that are neither Tier 1 nor Tier 2 events.

For both Tier 1 (if any are identified later) and Tier 2 events, the 95% CIs for the difference in percentage of participants reporting the events between the 2 comparison groups will be calculated using the Miettinen and Nurminen method.

In addition, for Tier 1 events (if any are identified later), the asymptotic p-values will also be presented for the difference in percentage of participants reporting the events between the 2 comparison groups, based on the same test statistic and under the assumption that the test statistic is asymptotically normally distributed.

Descriptive summary statistics will be provided for Tier 3 events for each study arm.

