| Secondary (Immunogenicity) | To demonstrate that the SARS-CoV-2 immune response elicited by CCI BNT162b2 (Omi XBB.1.5) is noninferior to that elicited by BNT162b2 (Omi XBB.1.5) alone (Cohort 3) | SARS-CoV-2 (Omi XBB.1.5)— neutralizing titers | In evaluable immunogenicity participants: • GMR of SARS-CoV-2— neutralizing titers at 4 weeks after vaccination in participants who received BNT162b2 (Omi XBB.1.5) to those who received BNT162b2 (Omi XBB.1.5) alone |
| Secondary (Immunogenicity) | To demonstrate that the HAI immune response elicited by CCI BNT162b2 (Omi XBB.1.5) is noninferior to that elicited by CCI alone (Cohort 3) | HAI titers (from HAI based on Colderived virus) for the matched seasonal strains (CCl recommended by WHO | In evaluable immunogenicity participants: • GMR of HAI titers at 4 weeks after vaccination in participants who received CCI BNT162b2 (Omi XBB.1.5) to those who received CCI alone |
| Secondary (Immunogenicity) | To demonstrate that the HAI immune response elicited by CO BNT162b2 (Omi XBB.1.5) is superior to that elicited by QIV administered concomitantly with BNT162b2 (Omi XBB.1.5) (Cohort 2) | HAI titers (from HAI based on Colderived virus) for the matched seasonal strains (CCI recommended by WHO | In evaluable immunogenicity participants: GMR of HAI titers at 4 weeks after vaccination in participants who received CCI BNT162b2 (Omi XBB.1.5) to those who received QIV administered concomitantly with BNT162b2 (Omi XBB.1.5) The difference in percentage of participants with seroconversion to the seasonal strain (CCI at 4 weeks after vaccination between participants who received CCI BNT162b2 (Omi XBB.1.5) and those who received QIV administered concomitantly with BNT162b2 (Omi XBB.1.5) |

- a. Seroconversion is defined as having an HAI titer <1:10 prior to vaccination and ≥1:40 at the postvaccination time point of interest, or an HAI titer of ≥1:10 prior to vaccination with a minimum 4-fold rise at the postvaccination time point of interest.

- b. Seroresponse is defined as achieving a postvaccination ≥4-fold rise from baseline (before the study vaccination). If the baseline measurement is below the LLOQ, the postvaccination measure of ≥4 × LLOQ is considered seroresponse.

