5.2.2.2. Geometric Mean Ratio

Unadjusted GMR

The unadjusted GMR will be calculated as the difference in the means of logarithmically transformed assay results between 2 vaccine groups and exponentiating the difference. The 2-sided 95% CI will be obtained by exponentiating the limits of the CI for the mean difference of the logarithmically transformed assay results based on the t distribution.

Model-based GMR

The model-based GMR and associated 95% CI will be calculated by exponentiating the difference in LS means and the corresponding CIs based on the analysis of logarithmically transformed assay results using a linear regression model that includes the baseline assay results (HAI titer/SARS-CoV-2 NT), age, and vaccine group as covariates.

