6.1.2.2. Supplementary Analysis

Empirical RCDCs will be plotted separately for each strain by vaccine group. Bar charts with the numbers, proportions of participants achieving HAI seroconversion, SARS-CoV-2 seroresponse rate, and associated 95% CIs will be provided for each strain by vaccine group within each cohort. Further plots of GMTs and/or GMFRs may also be done.

Additional model-based GMRs and associated 95% CIs based on a linear regression model (as specified in Section 5.2.2.2) may also be provided. Adjusted difference in percentage of participants with seroconversion/seroresponse at 4 weeks after vaccination and the associated 2-sided 95% CIs may also be calculated using the statistical methods described in Section 5.2.1.

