6.2.2. Supplemental Analysis

Empirical RCDCs will be plotted separately for each strain by vaccine group. Further plots of GMTs and/or GMFRs may also be done.

Additional model-based GMRs and associated 95% CIs based on a linear regression model (as specified in Section 5.2.2.2) may also be provided. The adjusted difference in percentage of participants with seroconversion at 4 weeks after vaccination and the associated 2-sided 95% CIs may also be calculated using the statistical methods described in Section 5.2.1.

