Appendix 1. List of Abbreviations

| AE AESI BMI BNT162b2 CI COVID-19 CRF e-diary EDMC | adverse event of special interest body mass index Pfizer-BioNTech COVID-19 vaccine confidence interval coronavirus disease 2019 case report form electronic diary external data monitoring committee Food and Drug Administration (United States) |
|---|---|
| BMI BNT162b2 CI COVID-19 CRF e-diary | body mass index Pfizer-BioNTech COVID-19 vaccine confidence interval coronavirus disease 2019 case report form electronic diary external data monitoring committee |
| BNT162b2 CI COVID-19 CRF e-diary | Pfizer-BioNTech COVID-19 vaccine confidence interval coronavirus disease 2019 case report form electronic diary external data monitoring committee |
| CI COVID-19 CRF e-diary | confidence interval coronavirus disease 2019 case report form electronic diary external data monitoring committee |
| COVID-19 CRF e-diary | coronavirus disease 2019 case report form electronic diary external data monitoring committee |
| CRF e-diary | case report form electronic diary external data monitoring committee |
| e-diary | electronic diary external data monitoring committee |
| | external data monitoring committee |
| EDMC | |
| | Food and Drug Administration (United States) |
| FDA | |
| GMC | geometric mean concentration |
| GMFR | geometric mean fold rise |
| GMR | geometric mean ratio |
| GMT | geometric mean titer |
| HA | hemagglutinin |
| HAI | hemagglutination inhibition assay |
| ICD | informed consent document |
| IRT | interactive response technology |
| IV | intravenous(ly) |
| LLOQ | lower limit of quantitation |
| LS | least square |
| MedDRA | Medical Dictionary for Regulatory Activities |
| mITT | modified intent-to-treat |
| N/A | not applicable |
| NI | noninferiority |
| NT | neutralizing titer |
| Omi | Omicron |
| CCI | |
| PT | preferred term |
| CCI | |
| QIV | quadrivalent influenza vaccine |
| QNS | quantity not sufficient |
| RCDC | reverse cumulative distribution curve |
| RNA | ribonucleic acid |
| SAE | serious adverse event |
| SAP | statistical analysis plan |
| SARS-CoV-2 | severe acute respiratory syndrome coronavirus 2 |
| SOC | system organ class |
| CCI | |
| WHO | World Health Organization |

Document Approval Record

| Document Name: | C5261002 Statistical Analysis Plan Clean Copy, V2, 16 May 202 |
|----------------|---|
| Document Name: | C5261002 Statistical Analysis Plan Clean Copy, V2, 16 May 202 |

Document Title:

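### As worded, SAP 5.2.1 stratifies the optional adjusted difference in HAI seroconversion by baseline neutralizing titer, not baseline HAI titer

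*SAP*

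**What the plan says.** SAP 5.2.1 first sets out the ordinary Miettinen and Nurminen interval for a between-group difference. It then adds "Another approach to calculate the adjusted difference in seroresponse rate or seroconversion rate between the 2 vaccine groups", which is "stratified by baseline NT category (< median, ≥ median) and age group (< median, ≥ median"). The cut-points are fixed the same way for both endpoints: "The median of baseline NTs and age will be calculated based on the pooled data in the 2 comparator groups". No alternative is given for HAI.

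Appendix 1 of the SAP has the entry "NT | neutralizing titer" and lists HAI as a separate term. SAP 2.2, footnote a, ties seroconversion to HAI: "Seroconversion is defined as having an HAI titer <1:10 prior to vaccination and ≥1:40 at the postvaccination time point of interest", or a fourfold rise from a baseline of at least 1:10.

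Two sections call the stratified rule. SAP 6.1.2.2 says that the adjusted difference for "seroconversion/seroresponse at 4 weeks after vaccination and the associated 2-sided 95% CIs may also be calculated using the statistical methods described in Section 5.2.1". SAP 6.2.2 does the same for "seroconversion at 4 weeks after vaccination and the associated 2-sided 95% CIs may also be calculated using the statistical methods described in Section 5.2.1"; there, seroconversion is the only binary endpoint. Neither section substitutes baseline HAI.

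For the model-based GMR, SAP 5.2.2.2 does distinguish the two assays: "baseline assay results (HAI titer/SARS-CoV-2 NT), age, and vaccine group as covariates".

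**The concern.** A supplementary adjusted difference normally serves to condition on a baseline variable that predicts the outcome. For seroconversion the natural candidate is baseline HAI, because the criterion itself depends on it: one threshold applies below 1:10 and another at or above it. The only neutralization assay in the readable text is the one for SARS-CoV-2 XBB.1.5. A programmer following SAP 5.2.1 would therefore stratify an influenza endpoint by a COVID-19 baseline.

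The consequence is narrow. Strata on a variable unrelated to the outcome are still valid under randomization, but they neither tighten the interval nor remove chance imbalance in baseline HAI. The adjusted seroconversion difference would also be conditioned on a different baseline from the adjusted HAI GMR that may be shown beside it.

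**Working it through.** **Text check**

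| Place | Endpoint | Baseline variable named |
|---|---|---|
| SAP 5.2.1, stratified difference | seroresponse and seroconversion | NT only |
| SAP 5.2.2.2, model-based GMR | HAI titers and SARS-CoV-2 titers | HAI titer or SARS-CoV-2 NT, by assay |
| SAP 6.4, subset analyses | influenza endpoints | HAI, <1:10 vs ≥1:10 |
| Protocol 9.3.1.4, model-based GMR | all GMRs | neutralizing titer only |

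Within the SAP, the binary rule is the only adjusted analysis that does not match the assay.

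**Size.** The plan states no figure on this point, so there is none to reproduce.

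Inputs:
- Arm sizes n₁ = 2000 and n₂ = 1000, the Cohort 2 HAI subset in protocol 9.5.1.
- Assumed: q, the share with baseline HAI ≥1:10, from 0.30 to 0.70.
- Assumed: p₀ and p₁, the seroconversion rates below and at or above 1:10, each from 0.10 to 0.90 and 0.10 to 0.40 apart in either direction. The same rates apply in both arms.

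Formulas:
- p = (1−q)p₀ + q·p₁
- Unstratified SE = √[p(1−p)(1/n₁ + 1/n₂)]
- Share of variance removed by HAI strata: R = q(1−q)(p₁−p₀)² / [p(1−p)]
- SE reduction = 1 − √(1−R)
- One-SD chance imbalance in the HAI split = √[q(1−q)(1/n₁ + 1/n₂)]
- Shift in the difference = imbalance × |p₁−p₀|

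Worked case, q = 0.5, p₀ = 0.90, p₁ = 0.50:
- p = 0.70; SE = √(0.21 × 0.0015) = 1.77 points.
- R = 0.25 × 0.16 / 0.21 = 0.190; SE reduction = 1 − √0.810 = 10.0%.
- Imbalance = √(0.25 × 0.0015) = 1.94 points; shift = 1.94 × 0.40 = 0.77 points, or 0.77/1.77 = 0.44 SE.

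Grid in steps of 0.05 (1512 combinations):

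| Gap between baseline categories | SE reduction |
|---|---|
| 10 points | 0.4–1.0% |
| 20 points | 1.7–3.3% |
| 30 points | 3.9–6.5% |
| 40 points | 7.0–10.5% |

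The minimum is 0.42% (q = 0.3, rates 45% and 55%). The grid maximum is 10.53% (q = 0.4, 10% and 50%). With q continuous the maximum is 10.56%, at q = 0.375: R = 0.0375/0.1875 = 20%. If all rates lie within 30–70%, the range is 0.4–8.3%. Across the grid the unstratified SE is 1.30–1.94 points, the one-SD imbalance 1.77–1.94 points, and the shift 0.18–0.77 points (0.09–0.45 SE).

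**The rule as written against the matched rule.** The formulas compare HAI strata with no strata. A simulation of the worked case (3000 trials, NT independent of HAI) adds the NT rule. The SD of the estimate was 1.76 points unadjusted, 1.76 with NT × age strata and 1.60 with HAI × age strata. Over five scenarios, one of them with a latent NT–HAI correlation of 0.3, the absolute correlation of the estimate with baseline HAI imbalance was 0.12–0.43 unadjusted, 0.12–0.42 with NT strata and at most 0.03 with HAI strata. In these scenarios the NT strata did essentially nothing for seroconversion.

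**The case against.** The strongest reply is that this is loose wording rather than a chosen analysis. Protocol 9.3.1.4 names only a baseline neutralizing titer, although protocol 9.3.2 and 9.3.3 apply that section to HAI GMRs too. SAP 5.2.2.2 restates the same covariate by assay. NT in SAP 5.2.1 may be the same shorthand, left uncorrected. This is plausible and may well be the intent, but SAP 5.2.1 does not say so, and the SAP keeps the two terms apart elsewhere. The wording needs correcting on either reading.

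The second reply is that nothing depends on it. This stands in full. The main analyses in SAP 6.1.2.1 and 6.2.1 use the unadjusted GMR and the Miettinen and Nurminen difference without strata, and the decision rules in SAP 5.1 do not use the adjusted result. Baseline HAI can also be examined through the optional subset analyses in SAP 6.4.

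The third reply is that the size rests on assumptions and on a 1:10 split rather than the pooled median. This also stands: apart from the arm sizes, every input is assumed, and the upper end needs a 40-point gap. It limits what can be said about the amount of precision lost, but does not affect the textual point.

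**Conclusion.** The concern holds and is minor. As worded, the rule names the wrong assay's baseline for HAI seroconversion; whether a matched baseline was intended cannot be settled from the text. Noninferiority and superiority conclusions, type I error and power are unaffected, and no bias is expected. The cost falls on an optional estimate: an SE larger by an amount that stratifying on baseline HAI would cut by 0.4–10.6%, and an uncorrected shift of about 0.2–0.8 points for a one-SD chance imbalance. These sizes assume the ranges given above, a split at 1:10, equal rates in the two arms and a baseline NT that tells little about baseline HAI. HAI strata would remove only imbalance in the split used; differences in titer within the ≥1:10 group would remain.

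**What to change.** In SAP 5.2.1, replace the baseline NT category with *baseline assay result category (strain-specific HAI titer for seroconversion; SARS-CoV-2 NT for seroresponse)*, change the sentence on medians to match, and state the HAI cut-point before unblinding.

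The cut-point is the sponsor's choice. If the pooled median is kept, the SAP should say how ties are handled. Protocol 9.1.1 sets results below the LLOQ to half the LLOQ in the analyses. If that value is used for the categories and more than half of participants are below the LLOQ for a strain, the median equals it, the lower category is empty and the HAI factor drops out. The <1:10 vs ≥1:10 split already in SAP 6.4 is one option that avoids this.

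The cost is one revised rule in the SAP. It needs no new data and loses no participants, because seroconversion status already requires a prevaccination HAI titer. Separately, SAP 2.1 reports no modification to the protocol's analysis plan, although the GMR covariate in SAP 5.2.2.2 differs from protocol 9.3.1.4; that could be recorded in the same revision.

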## 2.3.1. Risk Assessment

Potential Risk of Clinical Significance	Summary of Data/Rationale for Risk	Mitigation Strategy
Study In	tervention(s): Selected CCI BN	T162b2 (Omi XBB.1.5) and CC BNT162b2 (Omi XBB.1.5)
Local and systemic reactions to the vaccine may occur (injection site redness, injection site swelling, and injection site pain; fever, fatigue, headache, chills, vomiting, diarrhea, muscle pain, and joint pain) following vaccination.  Other key risks identified for BNT162b2, and therefore for the combination vaccine candidates, are lymphadenopathy; hypersensitivity reactions, such as rash, pruritus, urticaria, angioedema, and anaphylaxis; and myocarditis and pericarditis. 40	reactions seen with other vaccines, 41 as well as the COVID-19 vaccine BNT162b2, which is also based on modRNA	The study employs the use of a reactogenicity e-diary, which allows the investigator to monitor local reactions and systemic events in real time after each vaccination through an electronic portal. Severe reactions will require an unscheduled telephone call, and visit if required, to be conducted per protocol.  All study participants will be observed for at least 30 minutes after vaccination.
The safety and efficacy profile of a novel vaccine is not yet fully characterized.	novel vaccines, they are based on the same platform (modRNA) as the COVID-19 vaccine BNT162b2, which has been shown to have a positive benefit/risk profile.	AE and SAE reports will be collected from the signing of the ICD through 4 weeks and 6 months, respectively, after vaccination.  CCI  while the AESIs of myocarditis/pericarditis will be collected from vaccination through 6 weeks after vaccination.  All participants will be observed for at least 30 minutes after vaccination.

Potential Risk of Clinical Significance	Summary of Data/Rationale for Risk	Mitigation Strategy			
	Study Intervention(s): BNT162b2 (Omi XBB.1.5)				
that of BNT162b2, ie, local reactions, such as injection site redness, injection site swelling, and injection site pain, and systemic events, such as fever, fatigue, headache, chills, vomiting, diarrhea, muscle pain, and joint pain.  Other key risks identified for BNT162b2 are lymphadenopathy;					

Potential Risk of Clinical Significance	Summary of Data/Rationale for Risk	Mitigation Strategy			
	a short time following standard treatment and rest. Healthcare professionals should be alert to the signs and symptoms of myocarditis and pericarditis in vaccine recipients.				

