#### 8.4.8. Adverse Events of Special Interest

The following events are protocol-specified AESIs and are collected from vaccination through 6 months after vaccination unless otherwise specified:

- Confirmed diagnosis of myocarditis or pericarditis occurring after Visit 1 through 6 weeks after vaccination. See Section 8.10.6.
- Potential menstrual cycle disturbances occurring after Visit 1 through 6 months after vaccination. See Section 8.10.7.

Protocol-specified AESIs are examined as part of routine safety data review and signal detection processes and procedures throughout the clinical trial. Should an aggregate analysis indicate that these prespecified events occur more frequently than expected, eg, based on epidemiological data, literature, or other data, then this will be submitted and reported in accordance with Pfizer's safety reporting requirements. Aggregate analyses of safety data will be performed on a regular basis per internal SOPs.

All protocol-specified AESIs must be reported as an AE or SAE following the procedures described in Sections 8.4.1 through 8.4.4. An AESI is to be recorded as an AE or SAE on the CRF. In addition, an AESI that is also an SAE must be reported on the Vaccine SAE Report Form or via PSSA.

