6.1.1.2.2. Sensitivity/Supplementary Analysis

To support the interpretation of the main analysis results, descriptive summary statistics will also be provided by vaccine group for related AEs, severe AEs, and protocol-specified AESIs (defined in Section 8.4.8 of the protocol).

Immediate AEs (within the first 30 minutes after vaccination) will also be descriptively summarized for each vaccine group if the number of immediate AEs is sufficiently large; otherwise, they may be listed only.

Symptoms and measurements collected at cardiac evaluation visits for monitoring of potential myocarditis or pericarditis will be presented in a listing, regardless of whether there is a confirmed diagnosis.

All AEs that were collected before vaccination or more than 4 weeks after vaccination (outside of the reporting period) may not be included in the AE summary tables but will be included in the AE listings.

Figures:

A forest plot for the percentage differences and associated 2-sided 95% CIs of Tier 2 events may be presented.

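### With no Tier 1 events listed, the plan guarantees no between-arm difference with a confidence interval for its own AESIs and named key risks when each preferred term stays under 1%

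*SAP*

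**What the plan says.** SAP 5.2.1 and protocol 9.3.1.1 sort AEs into three tiers.

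- **Tier 1** is for prespecified, clinically important events, listed in a separate safety review plan. The SAP reports that "there is no Tier 1 event identified for the study interventions at this stage".
- **Tier 2** is any other MedDRA preferred term for which "there are at least 1% of participants in at least 1 study arm reporting the event".
- **Tier 3** is everything else.

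The tiers decide the output. The SAP provides a between-arm interval for the first two: "For both Tier 1 (if any are identified later) and Tier 2 events, the 95% CIs for the difference in percentage of participants", by the Miettinen-Nurminen method. For the third, "Descriptive summary statistics will be provided for Tier 3 events for each study arm". SAP 6.1.1.2.1 gives the arm pairs for Tier 2: A vs B, C vs D, and E vs each of F, G and H. SAEs are summarised descriptively.

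The protocol names certain risks in advance. Section 8.4.8 lists two AESIs: "Confirmed diagnosis of myocarditis or pericarditis occurring after Visit 1 through 6 weeks after vaccination" and "Potential menstrual cycle disturbances occurring after Visit 1 through 6 months after vaccination". The risk table in section 2.3.1 adds: "Other key risks identified for BNT162b2, and therefore for the combination vaccine candidates, are lymphadenopathy; hypersensitivity reactions" (rash, pruritus, urticaria, angioedema and anaphylaxis are given as examples), together with myocarditis and pericarditis.

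SAP 6.1.1.2.2 provides descriptive statistics by vaccine group for "related AEs, severe AEs, and protocol-specified AESIs". The same section says that AEs collected more than 4 weeks after vaccination may be left out of the AE summary tables and shown in listings.

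**The concern.** Describing safety is a primary objective, and these are the events that the protocol itself singled out. Whether any of them gets an estimated difference with an interval depends on an observed frequency, counted one preferred term at a time. Three features make a missing estimate likely.

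1. A rare event such as myocarditis will almost never reach 1%.
2. Hypersensitivity is a family of terms. Each term can stay under 1% while the family does not.
3. The 1% rule counts everyone in the arm, while menstrual disturbance can arise only in female participants.

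The time windows add a fourth gap. The AESI windows extend past the 4-week cut-off of the AE tables, and the SAP does not say that AESIs are exempt from it or which window the AESI summary covers.

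The reader of the study report would then have to work out the contrast for the risks of most interest, or the sponsor would have to produce it as an analysis that was not prespecified.

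**Working it through.** **Inputs.** Arm sizes follow from SAP 2.3:

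- Cohort 1: 450 at 2:1, so A = 300 and B = 150.
- Cohort 2: 4500 at 2:1, so C = 3000 and D = 1500.
- Cohort 3: 3600 at 2:2:1:1, so E = F = 1200 and G = H = 600.

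The Tier 2 threshold is 1% per preferred term (SAP 5.2.1). Rare-event rates of 0.01%, 0.05% and 0.1% come from protocol Table 8.

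**The plan's own figure.** Table 8 uses 1 − (1 − p)^n. For n = 3000 and p = 0.001 this is 1 − 0.999^3000 = 95.03%, printed as 95.0%. All 21 cells reproduce.

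**Tier 2 trigger counts**, as 1% of n rounded up: A 3, B 2, C 30, D 15, E and F 12, G and H 6.

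**Chance that a preferred term triggers Tier 2 in at least one arm of a cohort.** The formula is 1 − Π P(X_arm < trigger), with X binomial, arms independent and the same true rate in every arm:

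| True rate | Cohort 1 | Cohort 2 | Cohort 3 |
|---|---|---|---|
| 0.1% | 1.4% | 8 × 10⁻¹¹ | 0.008% |
| 0.5% | 33% | 1.0% | 19% |
| 1% | 77% | 78% | 96% |
| 2% | 99% | ~100% | ~100% |

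So at 0.1%, Arm C will very probably see a case, and the rule will practically never produce a Cohort 2 contrast. At 1% or above it usually will.

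**Splitting across terms.** Take a family with a true rate of 2% in both Cohort 2 arms, divided equally over k preferred terms. The chance that a given term qualifies is about 100% for k = 1, 78% for k = 2, 10% for k = 3 and 1% for k = 4.

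**Female denominator.** Thirty cases in Arm C are 1% of the arm. If 40%, 50% or 60% of the arm is female (an assumption, since the documents give no figure), that is 30/1200 = 2.5%, 30/1500 = 2.0% or 30/1800 = 1.7% of the women.

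**What the missing interval could look like.** The counts below are illustrative. Intervals are Miettinen-Nurminen, C minus D, in percentage points:

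| Arm C (of 3000) | Arm D (of 1500) | Difference | 95% CI |
|---|---|---|---|
| 29, one term | 2 | 0.83 | 0.41 to 1.27 |
| 15, one of four terms | 3 | 0.30 | −0.12 to 0.66 |
| 60, the four terms together, different participants | 12 | 1.20 | 0.48 to 1.87 |
| 3, rare event | 0 | 0.10 | −0.16 to 0.29 |

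In every row each individual preferred term is Tier 3, because no term reaches 30 in Arm C or 15 in Arm D. The plan would therefore require none of these intervals.

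**Windows.** The AE tables may stop at 4 weeks. Myocarditis/pericarditis is collected to 6 weeks and menstrual disturbance to 6 months. Cases in the remaining time may appear only in listings, unless the AESI summary is read as covering the full window.

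**The case against.** A reader might infer that these risks can get no between-arm comparison at all. The documents do not support that. SAP 6.1.1.2.1 shows n, N, percentage and a 95% CI by vaccine group for all three tiers, and AESIs have their own summary by vaccine group, so the arms can be compared side by side. A named risk whose term reaches 1% in any arm becomes Tier 2. In the smaller arms that takes few cases: 2 in Arm B, 6 in Arm G or H.

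A reader might also infer that Tier 1 will be filled after the data are seen. The text allows later identification but does not say after unblinding, and the study team is to stay blinded to the end of the study. It is also true that no deadline is set. Nor is there a contradiction: nothing in the documents makes an AESI or key risk a Tier 1 event, the safety objective is descriptive, and no safety hypothesis is tested. The safety review plan that holds the Tier 1 list is not available here.

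Four further points carry some weight:

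- The AESI summary treats menstrual disturbance as a category, so splitting matters less there. It applies mainly to hypersensitivity.
- Myocarditis also has a cardiac-evaluation listing, review against expected frequency, and data monitoring committee oversight. None of these is planned as a between-arm estimate.
- The key risks are attributed to BNT162b2, which Arms B, D and F also receive, so a large difference from those arms is less expected.
- Intervals for very rare events are wide, as the 3 vs 0 row shows. A wide interval still states what the data can exclude.

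**Conclusion.** The point holds as a gap in what the plan guarantees. Any AESI or named key risk reported by under 1% per preferred term in every arm gets per-arm description only, with no between-arm difference and CI. For an event at 0.1% or less this is practically certain in Cohorts 2 and 3. Near 1% or above, a contrast is likely. Hypersensitivity can miss the threshold through splitting, and AESIs after week 4 may miss the AE summary tables.

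The trigger probabilities assume full enrolment at the planned ratios, independent arms and a common true rate. The documents give no expected rates for lymphadenopathy, hypersensitivity or menstrual disturbance, so whether these would reach 1% is unknown. The 29 vs 2 and 60 vs 12 counts show how the rule works and are not forecasts. This is a cheap improvement to a descriptive analysis; the safety objective does not fail without it.

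**What to change.** In SAP 5.2.1 and 6.1.1.2, and in protocol 9.3.1.1, before unblinding, prespecify the Miettinen-Nurminen difference and 95% CI for the following grouped terms, regardless of frequency and without p-values:

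- myocarditis/pericarditis, through 6 weeks;
- menstrual cycle disturbances, among female participants, through 6 months;
- hypersensitivity including anaphylaxis, over the 4-week AE window;
- lymphadenopathy, over the 4-week AE window.

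List the MedDRA terms that form each group. State that the 4-week table cut-off does not apply to the two AESIs. Use the arm pairs already in SAP 6.1.1.2.1; protocol 9.3.1.1 currently names only A vs B and C vs D, so the Cohort 3 pairs need adding there.

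The cost is SAP and protocol wording, agreement on the groupings, and four extra table rows per comparison from data already collected. The drawback is wide intervals for very rare events.
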